9.7 Offset Range (or Treatment Window)

The range of days when a treatment can be given.

- Visit 1 4: (+/-) 3 days
- Visit 5 6: (+/-) 7 days
- Visit 7: (+/-) 10 days
- Visit 8: (+/-) 21 days
- Visit 9: (+/-) 31 days

9.8 Off Study

Subjects will be considered off study when all planned treatment, early termination and follow-up visits have been completed, unless death or withdrawal of consent to continue participation occurs.

10.0 PHARMACOKINETIC STUDIES- Not for this study

- 10.1 Collection
- 10.2 Processing
- 10.3 Storage
- 10.4 Destruction

11.0 DATA AND SAFETY MONITORING PLAN

11.1 Identification of the DSMB obligated for oversight responsibilities

The University of Arizona Cancer Center Data Safety and Monitoring Board (DSMB) will provide ongoing oversight for this trial. This study has been assigned a high risk level by the DSMB.

11.2 Identification of the entity obligated for routine monitoring duties

Routine monitoring will be provided by the University of Arizona Cancer Center Quality Assurance/Quality Control (QA/QC) Program to ensure that the investigation is conducted according to protocol design and regulatory requirements.

This trial will also undergo real-time monitoring by the PI and study team, including documentation of real-time monitoring of any new or ongoing safety issues and regular meetings every month with the study team to review data and safety events. For individual participants, adverse events will be assessed every 4 weeks by the study coordinator according to the assessment schedule. A study-specific adverse event log will be reviewed and signed every four weeks by the PI. The PI will review all severe adverse events within 24 hours of reporting.

11.3 Monitoring progress and data review process

Routine monitoring of subject data will be conducted at least every month. The first routine monitoring visit will include at a minimum:

- Informed consent 100% of cases enrolled;
- Subject eligibility 100% of cases, up to three subjects;

• Data review – 100% of cases, up to three subjects.

All subsequent monitoring visits will consist of randomly selected subject cases based on current enrollment and include continuing review of previously selected cases, as applicable.

A monitoring visit report and follow-up letter will be completed approximately two weeks after the routine monitoring visit; a copy will be maintained in the study file. A query/finding form or an electronic record will also be completed by the monitor to request additional source documentation, clarification, information or corrections to the OnCore CRF and/or regulatory records. The Clinical Research Coordinator or other applicable staff responsible for the study will be given a copy of this form, or will be notified of the electronic record for resolution of queries/findings. The query/finding form will be maintained with a copy of the visit report for follow-up at the next monitoring visit. Electronic records will be available in the institution database or provided by the QA/QC Program staff.

The Principal Investigator will ensure the accuracy, completeness, legibility and timeliness of the data reported in the OnCore Case Report Form (CRF), or other acceptable data formats. Source documentation supporting the study data should indicate the subject's participation in the trial and should document the dates and details of study procedures, adverse events, and patient status.

Case report forms, which include the inclusion/exclusion criteria form, adverse event forms and serious adverse event forms *[other forms, depending on study]* should be completed via the institution database or other acceptable data formats. All subject forms and study files will be stored in a secure area limited to authorized staff.

Note: Routine monitoring of regulatory documents and test article will be conducted every three months.

11.4 Process to implement study closure when significant risks or benefits are identified

The PI will be advised of all study related AEs and will determine if the study at a certain point may need to be closed due the AEs.

Study stopping criteria will include the following:

- Death within 30 days after the investigational treatment at least possibly related to the study treatment.
- Any herpetic event or complication requiring hospitalization that is at least possibly related to the investigational agent within 30 days to treatment.

Individual treatment stopping criteria will include the following:

- 75% or greater number of TILs meeting criteria for withdrawal.
- Identification of high-risk feature in one or more TILs during study participation.
- Persistent discomfort (consecutive weeks of lesion pain, burning, or itching of Grade 2 or more).

11.5 Description of adverse events and reporting procedures

ADVERSE EVENTS

An adverse event (AE) is any untoward medical occurrence in a patient or clinical investigation subject administered a pharmaceutical product and that does not necessarily have a causal relationship with this treatment. An AE can therefore be any unfavorable and unintended sign, symptom, or disease temporally associated with the use of a medicinal (investigational) product, whether or not related to the medicinal (investigational) product.

Any and all adverse events will be recorded on the UMC adverse events record form and reviewed by the Principal Investigator.

All adverse events will be classified using either the MedDRA term or NCI Common Terminology Criteria for Adverse Events (CTCAE) 4.0 and will address:

- Grade
- Relationship to study drug (not related, unlikely, possible, probable, definitely)
- Causality other than study drug (disease related, concomitant medication related, intercurrent illness, other)
- Date of onset, date of resolution
- Frequency of event (single, intermittent, continuous)
- Event outcome (resolved, ongoing, death)
- Action taken (none, held, dose reduced, discontinued, medication given)

SERIOUS ADVERSE EVENTS

A serious adverse event (SAE) is any untoward medical occurrence that at any dose:

1) Results in death;

2) Is life-threatening;

- 3) Requires in-patient hospitalization or prolongation of an existing hospital stay;
- 4) Results in disability persistent or significant disability/incapacity, or:
- 5) Is a congenital anomaly/birth defect.

Note: A SAE may also be an important medical event, in the view of the investigator that requires medical or surgical intervention to prevent one of the outcomes listed above.

All serious adverse events, regardless of attribution, and any deaths will be reported within 24 hours of notification of the event to the sponsor and, if applicable, any collaborating entity. All serious adverse events and any deaths will be reported to the DSMB and to the University of Arizona Human Subjects Protection Program per the guidelines set forth in University of Arizona Cancer Center Data and Safety Monitoring Board Charter, Table 5: Adverse Event Reporting.

All serious adverse events will be processed by the DSMB Coordinator monthly for initial trend analysis and fully reviewed by the DSMB, every three months. The DSMB coordinator will review the SAE reporting process to confirm reporting requirements are met.

11.6 Plan for assuring data accuracy and protocol compliance

Routine study activity and safety information will be reported to the DSMB on a monthly basis, or more frequently if requested. These reports will include:

- Study activity, cumulative and for the period under review;
- Safety (narrative description on non-serious and serious adverse events, protocol pre-determined early stopping rules for safety or treatment-emergent adverse events);
- Predetermined protocol early stopping rules for efficacy/futility;
- Status of study in relationship to stopping rules;
- Current dose level of study agent;
- Routine monitoring and protocol compliance (describe the monitoring process and identify the status of the monitoring);
- Comments;
- Attachments (AE data reviewed by the PI to compile the report, SAE letters and reports, results of any review(s), applicable correspondence with the IRB or other regulatory agencies

Data, safety and study progress will be reported to:

- Human Subjects Protection Program (IRB) at least annually;
- Sponsor (if applicable) at least quarterly.

11.7 Identification of the sponsor or funding agency, as applicable

The PI will immediately notify; in writing, the funding agency, if applicable, any action resulting in a temporary or permanent suspension of the study. A copy of this correspondence will also be forwarded to the DSMB and the SRC.

12.0 ADDITIONAL SAFETY REPORTING REQUIREMENTS

Safety Reporting to Amgen

The Investigator is responsible for compliance with expedited reporting requirements for serious, unexpected and related adverse events (SUSARs), for

generation of SAE reports including narratives, and for periodic reporting to Amgen of SAEs as outlined in Table 8 and Table 9 below. Individual safety reports (Table 8) should be accompanied by the Fax Cover Form provided in Appendix C, and sent to Amgen Global Safety, utilizing the fax or email information provided on the cover page. Aggregate safety reporting (Table 9) including listings, tabulations and summary reports should be scanned and accompanied by the Fax Cover Form provided in Appendix C, and sent to Amgen NASCR, utilizing the email information provided on the cover page. In addition to the requirements outlined in Table 8 and 9, Investigators are required to report **direct exposures** to talimogene laherparepvec (e.g., needle stick, splash back) of herpetic illness and **all suspected herpetic events** (refer to Section 13.0 'Accidental Exposures to Talimogene Laherparepvec and Herpetic Events').

Table 8.	Expedited	Reporting	Requirements	for Interventional	l Studies

Safety Data	Timeframe for Submission to Amgen
Suspected Unexpected Serious Adverse Reaction (SUSARs)	Individual reports sent to Amgen at time of expedited reporting to IRB and/or FDA.
Serious Adverse Events (SAEs) (related)	Individual reports sent to Amgen at time of expedited reporting to IRB and/or FDA
Pregnancy/Lactation	Individual reports sent within 10 days of Sponsor/Investigator awareness. (Refer to Appendix C for Amgen template forms)

Individual reports should be faxed to [name] or scanned and sent via email to [contact]

Table 9. Aggregate Reports

Safety Data	Timeframe for submission to Amgen		
Adverse events (all serious and non-serious adverse events, regardless of relatedness)	Line listing and summary tabulation of all adverse events sent annually AND at end of study		
US IND Annual Safety Report	Annually		
Other Aggregate Analyses	At time of ISS sponsor submission		
(any report containing safety data generated during the course of the study)	-		

Final (Final of Otion) Damant in shudin m	At time of ISS sponsor submission to	
Final (End of Study) Report, including:	any body governing research	
 Unblinding data for blinded studies 	conduct (e.g., RA, IRB, etc.) but not	
 Reports of unauthorized use of a 	later than 1 calendar year after study	
marketed product	completion	
Aggregate reports should be submitted via amo	il to the Amaon NASCD menager	

Aggregate reports should be submitted via email to the Amgen NASCR manager, accompanied by the Fax Cover Form in Appendix C

13.0 Accidental Exposures to Talimogene Laherparepvic and Herpetic Event Reporting

In order to better assess and understand the potential risks to treated patients and/or third parties following the treatment of clinical trial subjects with talimogene laherparepvec, special reporting procedures apply for accidental exposures to talimogene laherparepvec and for suspected herpetic events. See Table 10 Accidental Exposure and Herpetic Event Reporting Requirement Summary'.

13.1 Accidental Exposure of HCPs to Talimogene Laherparepvec

HCPs involved in your clinical trial who were directly exposed to talimigene laherparepvec (e.g., needle stick, splash back) but who are without signs or symptoms of herpetic illness should be reported to Amgen at [name].

13.2 Suspected Herpetic Events

Suspected herpetic events must be reported to Amgen within 24 hours of

awareness. Reporting is required for: (1) suspected herpetic events in treated patients; (2) suspected herpetic events in at risk HCPs with direct or indirect exposure and 3) suspected herpetic events in treated patient's close contacts.

In addition to reporting these events, suspected herpetic lesions should be swabbed and submitted for qPCR testing for the detection of talimogene laherparepvec. Samples should be collected using appropriate technique and a flocked swab from site supplies. This test is likely to be more reliable if performed within the **first three days of symptom appearance**. Amgen does not require qPCR or other testing for wild type

HSV-1.

• Reporting Process for ISS Treated Patients:

- Any suspected herpetic lesion should be reported to Amgen at [name], evaluated by the Sponsor/Investigator and swabbed for qPCR testing.
- Once an initial report has been made, additional materials will be provided, including reporting forms and supplies needed for shipment of swab samples. Amgen will require patient consent for qPCR testing, which must be obtained prior to swabbing.

• Reporting Process for HCPs and Close Contacts:

 Sponsor Investigator should advise any HCPs and/or Close Contacts with suspected herpetic lesions to contact their personal provider to facilitate reporting to Amgen. Suspected herpetic lesions should be reported by the personal provider or exposed individual to Amgen at [name]. Once an initial report has been made, additional materials will be provided, including reporting forms and supplies needed for the shipment of swab samples. Amgen will require patient consent for qPCR testing, which must be obtained prior to swabbing.

Table 10. Accidental Exposure and Herpetic Event Reporting Requirement Summary

E	Dementen	Timeframe	Dement	Timing of	qPCR	Responsib	qPCR Test
Exposed Person	Reporter	for	Report	Swab	Testing	le Party	Result
		Reporting	Mechanism	Collection	Required	for Lesion	Distribution*
		to Amgen			?	Swabbing	
Treated Patients with suspected herpetic lesions	Sponsor / Investigator	Within 24 hours of Sponsor / Investigator awareness	Contact Amgen at [name] to report event	Collect swabs from suspected lesions ideally within 3 days of appearance of symptoms	Yes, if consent obtained	Sponsor / Investigat or	Sponsor / Investigator and Amgen

HCP directly exposed to product (e.g., needle stick, splash back) without signs or symptoms of herpetic illness	HCP's Personal Physician or impacted person	Within 24 hours of Reporter awareness	Contact Amgen at [name] to report event	N/A	N/A	N/A	N/A
HCP directly or indirectly exposed to product with suspected herpetic lesions	HCP's Personal Physician or impacted person	Within 24 hours of Reporter awareness	Contact Amgen at [name] to report event	Collect swabs from suspected lesions ideally within 3 days of appearance of symptoms	Yes, if consent obtained	HCP or HCP's Personal Physician	HCP's Personal Physician and Amgen
Close Contact (eg caregiver, spouse, child) with suspected herpetic lesions	Close Contact's Personal Physician or Close Contact	Within 24 hours of Reporter awareness	Contact Amgen at [name] to report event	Collect swabs from suspected lesions ideally within 3 days of appearance of symptoms	Yes, if consent obtained	Close Contact's Personal Physician	Close Contact's Personal Physician and Amgen

13. QUALITY ASSURANCE MEASURES

Per the UACC DSMB Charter, Internal Ad Hoc audits may be performed on any UACC clinical trial if identified for audit, the audit will be conducted by an identified audit team per the UACC DSMB Charter. A QA/QC representative will coordinate the audit team functions and a written audit report will be provided to the principal investigator and the DSMB

14. MODIFIED RECIST CRITERIA – Appendix B

15. REMOVAL OF SUBJECTS

Subjects have the right to withdraw from the study at any time and for any reason without prejudice to their future medical care by the provider or at the institution. If this occurs, the investigator, or designee, is to discuss with the subject the safe and appropriate processes for discontinuation from the investigational product, intervention or device.

Subjects that wish to discontinue active IP treatment/intervention/device may elect to continue with the other protocol required assessments. The investigator should discuss with the subject the options for continuation of the study schedule of assessments (i.e. blood work, scans, physical exams, diaries) and collection of data, including endpoints and adverse events.

The investigator or designee must document the change in status of the subject's participation in the study and as applicable, the level of follow up that is agreed to by the subject (i.e. agrees to follow up exams, adverse event review, phone contact, but not to further treatment and/or procedures).

Subject withdrawal of consent for a study indicates that the subject does not wish to receive further protocol required therapies or procedures, and the subject does not wish to, or is unable to continue further study participation. Subject data only up to the time when consent is withdrawn will be included in the analysis of the study.

16. STATISTICAL CONSIDERATIONS

16.1 Analysis Endpoints

16.1.1 Primary Endpoint

The primary end point is to evaluate the overall response rate (ORR) defined as proportion of subjects who achieved CR and PR in the cSCC TILs. Clinical assessments will be done using a ruler or calipers. Digital photograph of the lesion(s) will be recorded each visit. Through clinical evaluation, CR will be defined as the complete disappearance of all TILs and PR will be defined as at least a 30% decrease in the sum of the diameters of TILs, taking as reference the baseline sum diameters. Progression is defined as >20% increase of at least 5 mm in the sum of the longest diameter recorded or increase in tumor burden \ge 20% relative to nadir (minimum recorded tumor burden) or the appearance of recurrent lesions confirmed by an assessment 8 weeks after the end of the injections (Visit 6). Stable disease (SD) is defined as decrease in tumor size <30% or an increase in size <20%.

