9.4.1.1 Tumor Response

Complete Response (CR): Complete disappearance of all TILs (whether measurable or not, and no new lesions at the site of injection) confirmed by an assessment 8 weeks after the end of the injections (Visit 6).

Partial Response (PR): Decrease in tumor burden $\ge 30\%$ relative to baseline confirmed by an assessment 8 weeks after the end of the injections (Visit 6).

Duration of Overall Response (DOR): DOR is when the time measurement criteria are met for CR or PR (whichever status is recorded first) until the first date that recurrence or progressive disease (PD) is objectively documented, taking as reference for PD the smallest measurements recorded since the treatment started. If no recurrence or PD is documented after PR or CR is observed the time measurement will be performed at Visit 6 for PR and Visit 8 for CR.

Durable Response Rate (DRR): Measured from the time measurement criteria are met for CR or PR (whichever status is recorded first) with the response lasting continuously for > than or equal to 6 months. For PD, the reference will be the
smallest measurements recorded since the treatment started.

Time to progression (TTP): This will be measured from the time treatment is initiated until the first date that recurrence or progressive disease (PD) is objectively documented, taking as reference for PD the smallest measurements recorded since the treatment started.

Progressive Disease (PD): Progression is defined as >20% increase of at least 5 mm in the sum of the longest diameters of the target lesions or increase in tumor burden $\ge 20\%$ relative to nadir (minimum recorded tumor burden) or the appearance of one or more new lesions confirmed by an assessment 8 weeks after the end of the injections (Visit 6).

• **Rapid PD (RPD):** Is defined as an increase of >50% in tumor burden for lesions >2 cm in diameter or 100% tumor burden increase for lesion ≤2cm between visits.

Stable Disease (SD): Not meeting criteria for CR or PR, in absence of PD (Decrease of tumor size <30% to increase in size <20% of less than 5 mm in the sum of the longest diameters of the target lesions).

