9.4.1.2 Clinical Management of TILs and TNILs

Along with assessing the overall tumor response (see Section 9.4.1.1, Tumor Response), each individual lesion will be assessed to determine appropriate clinical management. The RECIST 1.1 (Appendix B) response criteria will also be used to evaluate each individual tumor response.

Individual Lesion Complete Response (IL-CR): Complete disappearance of target lesion (whether measurable or not, and no new lesion(s) at the site of the target lesion) confirmation by an assessment 8 weeks after the end of the injections (Visit 6).

Individual Lesion Partial Response (IL-PR): Decrease in tumor burden $\ge 30\%$ relative to baseline confirmed by an assessment 8 weeks after the end of the injections (Visit 6).

Individual Lesion Progressive Disease (IL-PD): Progression is defined as >20% increase of at least 5 mm in the sum of the longest diameters of the target lesions or increase in tumor burden $\ge 20\%$ relative to nadir (minimum recorded tumor burden) or the appearance of one or more new lesions confirmed by an assessment 8 weeks after the end of the injections (Visit 6).

 Individual Lesion Rapid PD (IL-RPD): Is defined as an increase of >50% in tumor burden for lesions >2 cm in diameter or 100% tumor burden increase for lesion ≤2cm between visits.

Individual Lesion Stable Disease (IL-SD): Not meeting criteria for CR or PR, in

absence of PD (Decrease of tumor size <30% to increase in size <20% of less than 5 mm in the sum of the longest diameters of the target lesions).

	Individual Lesion	Individual	Progressive Disease	Stable Disease
	Complete Response	Lesion Partial	(PD)	(SD)
	(IL-CR)	Response (IL-		
	IL-CR to be	PR)		
	determined at the latest by Visit 6 (8	 IL-PR will be followed and assessed at 	 If IL-PD confirmed in two consecutive visits OR at Visit 6 (8 week 	 IL-SD will be followed and assessed up to
	week follow up), and will be followed for 6	assessed at Visit 6 (8 week follow up)	OR at Visit 6 (8 week follow up), TIL will be withdrawn and	assessed up to Visit 6 (8 week follow up)
	months • No additional	 If IL-SD is documented at 	alternative therapeutic intervention given	 Alternative therapeutic

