	 injections will be given to TILs who have achieved IL-CR prior to the 4th injection visit If recurrent at any 	Visit 6 or beyond, alternative therapeutic intervention will be offered	 If subject has additional TILs, will continue study participation If subject has only one, subject will be 	intervention will be offered if no IL-CR or IL-PR is observed by Visit 6.
TILs	point after IL-CR has been documented, then alternative therapeutic intervention offered (surgical excision, radiation, intralesional therapy etc.) based on patient preference	• If IL-PR continues, TIL will be closely followed until Visit 8, where alternative therapeutic intervention will then be offered	 withdrawn If IL-RPD occurs, treatment will be deferred that visit and will be reevaluated next visit. o If IL-PD confirmed, lesion withdrawn from study and alternative 	
			therapeutic intervention ○ If subject has more than one TIL, then lesions will continue to be a part of the study	
TNILs	 IL-CR to be determined at the latest by Visit 6 (8 week follow up), and will be followed for 6 	• IL-PR will be followed and assessed up to Visit 6 (8 week follow up)	 IL-PD at Visit 3 will undergo alternative therapeutic intervention 	 IL-SD will be followed and assessed up to Visit 6 (8 week follow up)
	monthsIf recurrent at any	 Alternative therapeutic 		 Alternative therapeutic

Table 7. Management of individual TILs and TNILs

point after IL-CR ha	s intervention will	intervention will
been documented a	It be offered if no	be offered if no
Visit 6, then	IL-CR is	IL-CR is
alternative	observed by	observed by
therapeutic	Visit 6	Visit 6
intervention offered		

9.4.2 High Resolution Ultrasonography of Squamous Cell Cancer:

The subjects will complete ultrasound assessments of their lesions at screening Visit (0), and at Visit 6 (second follow up visit).

METHOD:

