16.1.2 Secondary Endpoints

 To assess the safety and adverse effect profile of talimogene laherparepvec in low risk cSCC. Adverse events to be assessed according to National Cancer Institute Common Terminology. This will be determined by incidence of all adverse events (AEs), grade ≥ 3 AEs, safety adverse events (SAEs), and events requiring the discontinuation of study drug, local effects on the tumor (ie, pain, inflammation and ulceration), and any clinically significant laboratory values.

- 2. Time to response in cSCC TILS. Time to response is the time from first visit until objective tumor response (CR or PR) is identified
- 3. Duration of overall response (DOR) of TILs. This will be measured from the time measurement criteria are met for CR or PR (whichever status is recorded first) until the first date that recurrence or progressive disease (PD) is objectively documented, taking as reference for PD the smallest measurements recorded since the treatment started. If no recurrence or PD is documented after PR or CR is observed the time measurement will be performed at Visit 8.
- 4. Durable response rate of TILs. The duration of overall response is ORR lasting continuously for > than or equal to 6 months.
- 5. Time to progression (TTP) of TILs. This will be measured from the time treatment is initiated until the first date that recurrence or progressive disease (PD) is objectively documented, taking as reference for PD the smallest measurements recorded since the treatment started.
- 6. Overall response rate (CR+PR) of TILs assessed by imaging technique (high frequency ultrasound) and correlate it with clinical overall response rate.
- 7. Overall clinical response rate (CR+PR) of individual TILs injected with talimogene laherparepvec (not as overall subject response). Overall response rate is defined as the proportion of injected lesions which achieved complete and partial response.

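### Sections 16.1 and 16.2 do not say how to score a TIL sent to non-study therapy under Table 7, so DOR, durable response and TTP, and in a few subjects the Visit 6 ORR, can credit that therapy to T-VEC

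*Combined protocol and SAP*

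**What the plan says.** **Scoring.** Section 16.1.1 takes CR as the disappearance of all TILs. For PR it says: "PR will be defined as at least a 30% decrease in the sum of the diameters of TILs". Subject-level PD is also sum-based: growth in the summed diameters or in tumor burden relative to nadir, or the appearance of recurrent lesions. Section 9.4.1.1 and Appendix B work the same way. Section 16.2 includes every subject with at least one dose in the efficacy analysis.

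**Lesion management (section 9.4.1.2, Table 7).** There are three routes to other therapy by or after Visit 6:
- "If IL-PD confirmed in two consecutive visits", or at Visit 6, the TIL is withdrawn and given other therapy. For the subject, "If subject has additional TILs, will continue study participation".
- A TIL that was IL-PR and is IL-SD at "Visit 6 or beyond, alternative therapeutic intervention will be offered".
- For a TIL that is IL-SD, "intervention will be offered if no IL-CR or IL-PR is observed by Visit 6".

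**Time endpoints.** Under 16.1.2, DOR and TTP end at documented recurrence or PD. For DOR: "If no recurrence or PD is documented after PR or CR is observed the time measurement will be performed at Visit 8". Section 3.2 agrees. Section 9.4.1.1 differs: "time measurement will be performed at Visit 6 for PR and Visit 8 for CR". The only explicit censoring rule in section 16 is in 16.2.6 and covers non-responders in the time-to-response analysis.

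**Stopping.** The first individual criterion in section 11.4 is "75% or greater number of TILs meeting criteria for withdrawal". The other two are a high-risk feature in a TIL and persistent discomfort.

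**The concern.** TILs reach non-study therapy because T-VEC did not control them. If such a lesion then counts as 0 mm, another treatment produces the shrinkage. If it is dropped from both baseline and follow-up sums, the failing lesion leaves the result. Either way the subject looks better than T-VEC alone made them.

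The time endpoints are the more exposed. A stable TIL can be treated elsewhere at Visit 6, and the subject's DOR or TTP clock keeps running, because that therapy is neither an event nor a censoring point. The primary endpoint is exposed by a narrower route, but the Simon rule in 16.2.1 turns on single subjects. In a single-arm trial, a scoring convention chosen after the data are seen could choose the outcome.

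**Working it through.** **Inputs.** Visit spacing is from section 2.4. Nominal days are V1 0, V2 21, V3 35, V4 49, V5 77, V6 105, V7 147, V8 245. Six months is taken as 183 days (assumption). The design is from 16.2.1: continue if at least 5 of 7 respond, success if at least 14 of 20. Lesion sizes below are illustrations, not trial data.

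**1. The plan's own figure.** P(success) = sum over x = 5 to 7 of b(x; 7, p) × P(Bin(13, p) ≥ 14 − x). At p = 0.50 this is 0.0417, and at p = 0.80 it is 0.812. The stated 0.05 and 80% reproduce, so the fault is in endpoint scoring and not in the design.

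**2. A TIL lost before Visit 6.** Two 12 mm TILs. A measures 12, 17, 18 mm at V1–V3: +5 mm (+42%), then +6 mm (+50%). That is IL-PD twice and below the 100% rapid-PD limit for lesions of 2 cm or less. A is withdrawn and excised. B measures 12, 11, 10, 9, 8, 8, 8, 8 mm at V1–V8. Sums at V1–V3 are 24, 28, 28, so the rise is 4/24 = +16.7% and there is no sum-level PD. One of two TILs withdrawn is 50%, below the 75% stopping criterion.

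| Scoring of A | V4 | V5 | V6 | V6 status | First PR | DOR to V8 (16.1.2) | DOR to V6 (9.4.1.1) |
|---|---|---|---|---|---|---|---|
| 0 mm | 9/24, −62.5% | 8/24, −66.7% | 8/24, −66.7% | PR | day 49 | 196 d | 56 d |
| Dropped from both sums | 9/12, −25% | 8/12, −33.3% | 8/12, −33.3% | PR | day 77 | 168 d | 28 d |
| Held at 18 mm | 27/24, +12.5% | 26/24, +8.3% | 26/24, +8.3% | SD | none | none | none |

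On the sum there is no TTP event by day 245, although A first met IL-PD on day 21.

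**3. A TIL treated at Visit 6.** A measures 12, 12, 12, 11, 11, 11 mm and B 12, 9, 7, 5, 5, 5 mm at V1–V6. Sums are 24, 21, 19, 16, 16, 16. The subject is PR from day 49 (16/24 = −33.3%). A is IL-SD and accepts the Visit 6 offer. Under 16.1.2, DOR runs 245 − 49 = 196 days, past 183. The time observed before other therapy is 105 − 49 = 56 days.

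**4. Longest span after Visit 6.** 245 − 105 = 140 days, and 140/245 = 57% of follow-up to the last measured visit. This is an upper bound, because the subject might have stayed free of progression without that therapy.

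**5. Effect on the decision.** Suppose exactly one of 20 subjects is like step 2, scored z = 0 or 1, and the other 19 respond with probability p.
- In stage 1: P = sum over x = 0 to 6 with x + z ≥ 5 of b(x; 6, p) × P(Bin(13, p) ≥ 14 − x − z).
- In stage 2: P = sum over x = 5 to 7 of b(x; 7, p) × P(Bin(12, p) ≥ 14 − x − z).

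| p | Stage 1, z = 0 / 1 | Difference | Stage 2, z = 0 / 1 | Difference |
|---|---|---|---|---|
| 0.50 | 0.0170 / 0.0663 | 4.9% | 0.0256 / 0.0578 | 3.2% |
| 0.65 | 0.1759 / 0.4043 | 22.8% | 0.2499 / 0.3645 | 11.5% |
| 0.80 | 0.6085 / 0.8631 | 25.5% | 0.7647 / 0.8241 | 5.9% |

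Each difference is the probability that go/no-go depends on the scoring, given one such subject.

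**6. The DOR conflict.** Under 9.4.1.1, the longest DOR for a PR without PD is V2 to V6: 105 − 21 = 84 days. Under 3.2 and 16.1.2 the same PR runs to V8: 245 − 21 = 224 days.

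**The case against.** The case for leaving this as a minor clarification has real weight.

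**Guards exist.** Appendix B reads best overall response only until progression, section 11.4 stops a subject with most TILs failing, and section 7.4 excludes some topical and injected drugs. None closes the gap. Subject-level PD is defined on the sum, so it need not occur. One of two TILs is below 75%. Excision and radiation are not on the excluded list.

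**Step 2 is delicate.** If B were 12 mm at V2, the sum would be 29/24 (+20.8%, +5 mm) and meet the PD size criteria. If B ended at 9 mm, the dropped reading would give 9/12 = −25%, which is SD. This stands: the example shows that the problem can arise, not how often.

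**0 mm is only one reading.** Withdrawing a lesion may simply mean it is no longer assessed, and radiation or intralesional therapy need not give 0 mm by Visit 6. This also stands, but the dropped reading still favours T-VEC.

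**Single-lesion IL-PD could be made the progression event.** That would replace the plan's sum-based PD, and it can clash with a later response. Take A at 10, 15, 15 mm and held at 15, with B at 19, 16, 12, 8, 6, 5 mm. Sums are 29, 31, 27, 23, 21, 20, so Visit 6 is PR (−31.0%). Response starts on day 105 and progression would be dated day 21, giving a DOR of −84 days. The fix below avoids this.

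**Conclusion.** The gap is real, and the plan should close it before results are read. Its main reach is DOR, durable response and TTP: nominally up to 140 of 245 days can follow non-study therapy. Visit 6 ORR is exposed only in subjects with two or more TILs who lose one to confirmed IL-PD before Visit 6 without sum-level PD. Their number is unknown, and the percentages in step 5 assume exactly one.

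The DOR end rule in 9.4.1.1 contradicts 3.2 and 16.1.2 whatever the frequency.

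Three stronger conclusions a reader might infer are not supported:
- *That therapy after Visit 6 also changes time to response.* Section 9.4.1.1 ties CR and PR to confirmation at Visit 6, so later excision should not create a new response.
- *That no PR could ever be durable.* The 84-day limit applies to DOR. Section 9.4.1.1 defines durable response separately, without a Visit 6 cut-off, and Table 7 follows a continuing IL-PR to Visit 8.
- *That the subject in step 3 is not durable.* The subject was already PR, and what would have happened after day 105 without other therapy is unknown.

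**What to change.** Add to sections 16.1 and 16.2:

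1. For ORR, individual-TIL response and time to response, a TIL given non-study therapy stays in all later sums at its last diameter before that therapy, and the subject cannot be CR. Subject-level PD stays sum-based, on these sums.
2. TTP is censored at the last assessment before the first non-study therapy to any TIL. A sensitivity analysis counts that therapy, or the confirmed IL-PD that led to it, as an event.
3. DOR is censored at the last assessment before any non-study therapy given to a TIL after response onset, with the same sensitivity analysis. If the therapy came before response onset, the TIL is held at its last diameter and DOR runs on that sum, so DOR cannot be negative.
4. A response is durable only if six months are observed before any post-response non-study therapy to a TIL.
5. Change 9.4.1.1 to Visit 8 for both CR and PR, and record the date, type and lesion of each non-study therapy.

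The cost is a short set of scoring rules in section 16, one corrected sentence in 9.4.1.1 and a small CRF addition. Clinical management, sample size, cut-offs and visits stay as they are. Some multi-TIL subjects will be scored slightly more conservatively, though responses in their other TILs still show in the individual-TIL rate. The censoring may be informative, which is why the sensitivity analysis is needed.
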